IRB Study Number: 20181032

Version 8, Date: 07/16/2021

Full Protocol Title: Preventing Cardiometabolic Disease in HIV-Infected Latino Men through a Culturally-Tailored Health Promotion Intervention

Protocol Number (eProst ID): 20181032

Protocol Version: 8

Protocol Version Date: 7/16/2021

PI Name: [name].

NCT number: NCT03839212

IRB Study Number: 20181032

Version 8, Date: 07/16/2021

1) **Protocol Title**

Preventing Cardiometabolic Disease in HIV-Infected Latino Men through a Culturally-Tailored Health Promotion Intervention

2) **IRB Review History***

This protocol has not been submitted for review by an external IRB.

3) **Objectives***

This study will address the following specific aims and test the following primary hypotheses:

Aim 1 (primary outcome): To evaluate the feasibility of recruitment, assessment procedures, retention, acceptability, and implementation of HOLA in a sample of midlife and older Latinos living with HIV.

Aim 2 (secondary outcome): To identify modifications needed in the design of a larger, confirmatory randomized controlled trial.

Aim 3 (secondary outcome): To explore changes in cardiometabolic risk factors (waist circumference, dyslipidemia, hypertension, and glucose), psychosocial functioning (depression and anxiety severity, social support), and health-related quality of life in a sample of midlife and older Latinos living with HIV enrolled in the HOLA health promotion intervention.

In addition, a career development and mentoring plan has been developed, comprised of expert mentorship, scholarly didactics and seminars, hands-on experience, as well as measurable productivity, including peer-reviewed manuscripts and an NIH grant application.

4) **Background***

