This study will not include women in that the specific research questions are targeted toward males. This study will specifically target Latinos. Individuals from other ethnic backgrounds are excluded as the study intervention is specifically tailored to address and target the specific needs and preferences of older Latinos with risk of cardiometabolic disease. This study is specific to only Latino males and will only report data on Latino males; findings from the study are intended to only be generalizable to Latino males. Both Black and White Latino males will be included in the study. We are not powered to detect differences between racial groups of Latino men. Previous research indicates that the outcomes in this study along with engagement with the intervention suggests no differences between racial groups of Latino males; no significant differences have been found in any outcomes in HOLA pilot data. We will use respondent self-report or self-identification to collect data on ethnicity and race. Though this application talks of racial/ethnic disparities and refers to Latino as an ethnicity, we are aware of the limitations of this construct. We acknowledge that ethnicity is a social construct and that Latinos are not a homogeneous, monolithic group even though the U.S. Census definition classifies them into one uniform ethnicity. Also, many racial/ethnic differences that have been identified in previous research are in fact confounded by socioeconomic status (SES). However, even though SES is indeed a central determinant of health status and overlaps with the concept of race, SES does not account for all racial health disparities.

6) **Number of Subjects***

18 older Latinos age 50+ will be enrolled.

7) **Study-Wide Recruitment Methods***

Recruitment procedures will protect participant confidentiality.

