conducted over the telephone. At 4 and 7 months after the initial interview, fasting blood samples will be drawn via venipuncture and stored at 4°C until analysis. HOMA will be calculated, providing a measure of insulin resistance. Study measures will be administered after the blood draws.

Assessment Measures

Cardiometabolic Risk: list of current medications, waist circumference, total cholesterol, HDL-C, LDL-C, triglycerides, blood pressure, and HbA1c, will be used to measure cardiometabolic risk.

Dementia Screen: The Mini Mental Status Exam (MMSE) will be used to screen for dementia. A Mungas-adjusted score of 23 or below indicates cognitive impairment.

Walking Ability: The 10 meter walk test will be used to evaluate walking ability, which has been used as a screening instrument to measure functional mobility and gait speed in physical activity interventions with older adults.

Demographics: The CLaRO Demographics Form will be used to collect demographic information (e.g., gender, education, income, preferred language, country of origin, time in the US, etc.) and will include a list of all diagnosed medical conditions and medications.

Acculturation: The 24-item Bidimensional Acculturation Scale (BAS) will be used to measure acculturation.

Depression Severity: The 20-item Center for Epidemiologic Studies Depression (CES-D) Scale and the 9-item Patient Health Questionnaire (PHQ-9) will be used to measure depression severity.

Anxiety Severity: The 7-item Generalized Anxiety Disorder (GAD-7) scale and the 14-item Perceived Stress Scale will be used to measure anxiety severity.

Social Support: Perceived social support will be measured using the 12-item Multidimensional Scale of Perceived Social Support (MSPSS).

Health Related Quality of Life: The SF-12 will be used to assess for health related quality of life.

Physical Activity: The 16-item Global Physical Activity Questionnaire (GPAQ) will be used to measure physical activity.

Stigma: The HIV Stigma Scale (HSS) is a 40 item measure of stigma and psychosocial aspects of having HIV.

IRB Study Number: 20181032

Version 8, Date: 07/16/2021

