As a pilot study, we will evaluate the feasibility of recruitment, assessment procedures, retention, acceptability, and implementation of HOLA in a sample of midlife and older Latinos living with HIV (**Aim 1**). Consistent with recommendations from biostatistical workgroups funded by NIH, this pilot study is not powered to test a hypothesis. This approach to analysis of feasibility data mirrors the structure of the first HOLA trial and other pilot trials conducted at the CNSA. Successful recruitment will be defined as meeting 100% of targeted sample (N = 18), with 20% or less of eligible subjects refusing to participate. Adequate retention will be defined as 85% or more of randomized subjects completing the post-intervention assessment. Acceptability is defined as 80% or more of sessions attended by subjects. To identify modifications needed in the design of a larger, confirmatory randomized controlled trial (**Aim 2**), we will use a project evaluation questionnaire developed by investigators at the CNSA and used in previous studies. The items are a mix of rating scales, yes/no questions, and open-ended questions that allow participants to give feedback in short answer format with specific interest in understanding the participants' opinions regarding the specific components of the intervention. To explore changes in cardiometabolic risk factors (waist circumference, dyslipidemia, hypertension, and glucose), psychosocial functioning (depression and anxiety severity, social support), and health-related quality of life (**Aim 3**), a one-way ANOVA will be used to illustrate the change in scores from baseline to post-intervention in all the outcome measures used.

A repeated measures ANOVA, as we have proposed, is appropriate to explore the intervention effects on cardiometabolic risk factors,

IRB Study Number: 20181032

Version 8, Date: 07/16/2021

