psychosocial functioning, and health-related quality of life given that this type of analysis is often used in studies that investigate either changes in mean scores over three or more time points. In the exploratory analyses, we will use age, SES, and years of education as covariates. In addition, a list of current medications will also be collected at baseline. Should the participants' medications be dose-adjusted, changed altogether, or if they are started on new medications such as statins, then we will adjust for them in them in the exploratory analysis as well. Covariates will be tested as moderators of treatment response.

Maintenance of Confidentiality:

Our staff is CITI certified and trained with maintenance of confidentiality. The information provided by study participants will be held as personal and confidential to the extent permitted by law. In addition to the safeguards included as part of the recruitment and screening process by assigning a patient a study ID to de-identify participants, all study participants will be given the contact information for the Principal Investigators to answer any questions that may arise. Participants will be informed that they may end their participation at any time without affecting access to any other services they may receive from the UM/JMMC Adult HIV Outpatient Clinic. All study procedures will be conducted according to good clinical practice and all other relevant regulatory guidelines.

All electronic data will be stripped of identifiers and stored in password-protected files on servers at the University of Miami Center on Aging. These data are password secured for minimal access to authorized personnel associated with the study. For each data file, a code number will be assigned, and the master list, linking code numbers with names, will be stored separately. At the conclusion of the project, the record linking the assigned research number and participant identity will be destroyed. Data will be entered into password secured databases by staff authorized by the principal investigator to do this, and they will abide by confidentiality regulations of the HSRO. No subject will be identified by any published report.

11) Provisions to Monitor the Data to Ensure the Safety of Subjects*

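### Aim 3 is analysed only by ANOVA on about 13 to 18 outcomes plus moderator tests, with no interval estimates, SD of change or multiplicity rule, in a pilot stated not to be powered for testing

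*Combined protocol and SAP*

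**What the plan says.** Section 6 (Number of Subjects) sets a single group: "18 older Latinos age 50+ will be enrolled". Sections 4 and 10 both disclaim power; in section 10 the words are "this pilot study is not powered to test a hypothesis". Section 3 (Objectives) nevertheless opens by saying that the study will "test the following primary hypotheses", and then lists three aims and no hypothesis. Aim 1 (feasibility) is labelled primary; Aim 3, on changes in risk factors, psychosocial functioning and quality of life, is labelled secondary and is framed as exploration.

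Section 10 gives the Aim 3 analysis in two forms. The first is that "a one-way ANOVA will be used to illustrate the change in scores from baseline to post-intervention in all the outcome measures used". The second reads: "A repeated measures ANOVA, as we have proposed, is appropriate to explore the intervention effects on cardiometabolic risk factors", and it is justified by the presence of three or more time points. The section then says "we will use age, SES, and years of education as covariates", with adjustment for medication changes, and ends: "Covariates will be tested as moderators of treatment response".

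The outcomes come from section 8 (Procedures Involved). For the cardiometabolic domain, "waist circumference, total cholesterol, HDL-C, LDL-C, triglycerides, blood pressure, and HbA1c, will be used to measure cardiometabolic risk"; HOMA is mentioned separately. The psychosocial and quality-of-life measures are CES-D, PHQ-9, GAD-7, the Perceived Stress Scale, MSPSS and SF-12. Physical activity (GPAQ) and HIV stigma (HSS) scales are also administered. Visits are at baseline, 4 months and 7 months.

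**The concern.** The inferential output of an ANOVA is an F test. An estimate with its uncertainty has to be asked for separately, and section 10 does not ask for one. Nor does it name a leading outcome within Aim 3, a significance level or a rule for the number of tests. A study that says it is not powered to test is therefore left with test statistics as its only stated Aim 3 result.

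At this sample size such results are unreliable in both directions. A few nominally significant changes among many outcomes may be chance, and a non-significant change does not show that nothing happened. The pilot is meant to precede a larger trial. What Aim 3 could usefully hand on is the size of each change, its interval, the SD of change and the correlation between visits.

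The two ANOVA descriptions also disagree. One covers baseline to post-intervention, the other three time points. A one-way ANOVA read as a comparison of independent groups would ignore that the same men are measured each time.

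**Working it through.** **Stated figure.** The only design figure is N = 18. The documents give no power, significance level, effect size or precision for it, so there is nothing to reproduce.

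**Assumptions.** Two-sided 5% level (not stated; 1% and 10% also shown), no true change in any outcome, and correlation between outcomes varied from 0 to 0.7.

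**Step 1: number of outcomes (section 8).**
- Cardiometabolic list as named: 7. Depression 2, anxiety 2, social support 1, quality of life 1. Total 7 + 2 + 2 + 1 + 1 = 13.
- Adding HOMA: 14. The values taken from records at baseline include insulin but not glucose, so a HOMA change from baseline is not clearly available.
- Splitting systolic and diastolic pressure: 15.
- Scoring SF-12 as two summaries (an assumption): 16.
- Adding GPAQ and HSS, which Aim 3 does not name: 18.

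**Step 2: chance of at least one nominally significant main result, independent outcomes.** Formula: 1 − (1 − α)^k.

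| k | α = 0.01 | α = 0.05 | α = 0.10 |
|---|---|---|---|
| 13 | 12.2% | 48.7% | 74.6% |
| 15 | 14.0% | 53.7% | 79.4% |
| 18 | 16.5% | 60.3% | 85.0% |

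**Step 3: correlated outcomes.** Simulated one-sample t tests on change scores (equivalent to a two-time-point repeated measures ANOVA), n = 18, α = 0.05, 40,000 runs, equal correlation ρ between all outcomes:

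| k | ρ = 0.2 | ρ = 0.3 | ρ = 0.5 | ρ = 0.7 |
|---|---|---|---|---|
| 13 | 46% | 43% | 34% | 26% |
| 15 | 50% | 47% | 37% | 27% |
| 18 | 56% | 52% | 41% | 30% |

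With 15 outcomes and a correlation of 0.5 within domains only, the figure is 43% to 47%, depending on how the domains are grouped.

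**Step 4: moderator tests.** The plan does not say how many there will be. If each of the three named covariates is tested for each of 15 outcomes, there are 15 × (1 + 3) = 60 tests, and 1 − 0.95^60 = 95.4% if independent. Regressing change on three centred covariates (8,000 simulated runs) gives 89%, 81% and 66% at ρ = 0.3, 0.5 and 0.7. For 13 outcomes the simulated figures are 87%, 78% and 63%.

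**Step 5: what the sample can show for one outcome.** Paired t test, two-sided 5%; the unit is the SD of change. The CI half-width is t(0.975, n − 1)/√n. The plan's 85% retention target is 0.85 × 18 = 15.3, so 16 completers are also shown.

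| | n = 18 | n = 16 |
|---|---|---|
| Power for a true change of 0.5 SD | 0.516 | 0.465 |
| Change detectable with 80% power | 0.70 SD | 0.75 SD |
| 95% CI half-width | 2.110/√18 = 0.497 SD | 2.131/√16 = 0.533 SD |
| 95% CI for the SD, as a multiple of the estimate | 0.75 to 1.50 | 0.74 to 1.55 |

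A true change of 0.5 SD is thus missed 1 − 0.516 = 48% of the time with 18 complete men.

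**The case against.** The strongest reply is that the plan is already modest. Its verbs for Aim 3 are to illustrate and to explore, it calls the covariate work exploratory, and it sets no p-value threshold and promises no claim of significance. An exploratory ANOVA does not contradict a statement about power, and the hypothesis wording in section 3 looks like a loose lead-in. This stands in part: reading the ANOVA as a significance test is an inference, though a natural one, since the plan also speaks of intervention effects and of testing moderators. It does not answer the central point, because mild verbs do not say what will be reported.

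Three stronger readings are tempting, and the documents do not support them.
- *A false positive among the main results is more likely than not.* That needs a count towards the upper end of the range, a 5% level the plan never states, and near-independence. Overlapping scales (two for depression, two for anxiety, four lipid measures) make correlation likely. The figure passes one half comfortably only when moderator tests are counted.
- *The pilot produces no planning figures.* Aim 1 sets recruitment, refusal, retention and attendance criteria, and means and SDs could be drawn from the data. What is missing is any specification of intervals, SD of change and within-person correlation.
- *The later trial's endpoint and size would rest on chance.* Nothing says that Aim 3 p values will choose either; design changes are Aim 2, informed by a questionnaire.

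Banning p values outright would be a preference. Labelling them descriptive is enough.

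**Conclusion.** The point holds as a gap in the Aim 3 analysis. ANOVA and moderator tests are the only methods named, the two ANOVA descriptions do not agree, and no interval, SD of change or multiplicity rule is given. The chance of at least one nominally significant main result, 49% to 60%, rests on an assumed 5% level, independence and no true change; correlation lowers it, and moderator tests raise it. The 48% miss rate assumes 18 complete men and a paired analysis.

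The change should be made, but its weight is limited: Aim 3 is secondary and exploratory, and the primary feasibility aim is unaffected.

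**What to change.** In section 10, make estimation the Aim 3 analysis:
- For each outcome, report the within-man mean change from baseline at month 4 and at month 7 with a 95% CI, the SD of change and the visit-to-visit correlation.
- State that any p values are descriptive and that no outcome will be declared significant.
- Drop the moderator tests, or report them descriptively only.
- Replace the two ANOVA descriptions with one within-person analysis that covers both follow-up visits.
- List the outcomes, stating whether HOMA, GPAQ and HSS are among them and how blood pressure and SF-12 are scored.

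In section 3, delete the words "test the following primary hypotheses".

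The cost is wording. No data collection, visit or sample size changes. The sponsor gives up only significance statements that the plan says it is not powered to support. The intervals will be wide, about ±0.5 SD of change, and reporting them makes that visible.

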In addition, we will also collaborate with another study, the Clinic Registry Project (IRB#20160911), which serves as a consent to contact database, to contact eligible participants. They will provide us with contact information for participants in their study who have consented to be contacted by other studies. When contacting participants, the CHW will follow the phone script for calling UHealth consent to contact participants that has been tailored to this study.

8) **Procedures Involved***

Participants will be assessed at three time points (before starting the study, 4, and 7 months after the first interview) on measures of cardiometabolic risk factors (waist circumference, dyslipidemia, hypertension, and glucose), psychosocial functioning, and health-related quality of life.

All participants will read and sign an informed consent document and a HIPAA Research Authorization – Form B approved by the University of Miami Institutional Review Board (IRB). They will initially be provided with a verbal summary of the study and for those who appear to have problems reading the consent form it will be read aloud. Participant payments will be graduated. Participants will receive \$15 on the first visit, \$25 on the second visit, and \$35 on the third visit (total of honoraria = \$75).

Prior to starting the baseline assessments, blood draws will take place at the UM/JMMC Adult HIV Outpatient Clinic. Study staff will obtain initial HDL-C, LDL-C, triglycerides, insulin, and HbA1c levels via review of the electronic medical records. Trained and certified research assistants (RAs) who have at least a bachelor's degree will conduct all assessments in private offices at the UM/JMMC Adult Outpatient HIV Clinic, at a private interview room at the CTRS located on the 7th floor of the Don Soffer Clinical Research Center, or the participant's home. To ensure privacy in the home, we will conduct the interview in a private room with a door of the participant's choosing away from any common areas. In the event that there are other people in the house, the door can be closed to maintain privacy. In the event that an in-person interview is not feasible then the interview will be

IRB Study Number: 20181032

Version 8, Date: 07/16/2021

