Data will be collected using an Apple ipad with pre-programmed questionnaires. Data will be exported to SPSS for analysis. All electronic data will be stripped of identifiers and will be stored in password-protected files. For each data file, a code number will be assigned, and the master list, linking code numbers with names, will be stored separately. The data will be stored on password protected, network computer hard drives at the CNSA, which will only be accessible to the PI.

Blood samples will be stored at the University of Miami Center for AIDS Research Laboratory Sciences Core (D) at -80 °C until analysis. The labels on the blood

IRB Study Number: 20181032

Version 8, Date: 07/16/2021

sample tubes will not contain *participant ID numbers*. The blood samples will be stored in locked freezers in locked rooms within access-limited sections of the building.

All the data will be stored and secured using the procedure implemented by the Data Manager of the CNSA. The access to records and participants data will be allowed only to the study personnel.

Study data request goes through a web-based check-in and check-out procedure implemented by the CNSA. The Data Manager of the Center or designee monitors the logs. Upon de granting of the approval, the requester will either get the hard copy of the data or link to access the electronic data. All the data will not contain any identifying information.

Other parties interested in utilizing the samples for research will be required to provide a written protocol to the PI and the gatekeeper(s) for approval. Should samples be shared, no identifying information will be provided. Material Transfer Agreement will be negotiated between UM and the investigators requesting the data.

10) **Data Management***

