If a subject finds the research procedures to be upsetting or aversive, they will have the option to withdraw from the study. Participation will be completely voluntary, and will not affect the treatment they are receiving. Participants will be told that they may choose not to answer any questions and may decide to terminate the interview at any time. Research staff will be instructed to terminate interview sessions if participants appear to be stressed by the process. Additionally, the research staff will know how to link participants immediately with treatment personnel including case managers or therapists if participants appear to be stressed.

IRB Study Number: 20181032

Version 8, Date: 07/16/2021

13) Risks to Subjects*

The risks associated with participation in the study are deemed to be low and are outweighed by the potential benefits. Nevertheless, this study involves the administration of assessment instruments that may cause minor discomfort, and the risk of loss of confidentiality. All participants will be informed that information obtained in these interviews is confidential and that they can choose not to answer any questions. If participants feel uncomfortable during the research interview, they will be encouraged to take a break and to continue again later or will be asked if they want to stop the interview. The research assistant (RA) may also offer to call a case manager, another staff member, or concerned others (such as a close friend) to make sure the participant has someone to talk with about the interview. Some questions or tasks may cause some individuals to become uncomfortable. This has happened rarely with similar interview sessions. In fact, most participants experience the interview process in a positive way and enjoy the opportunity to be heard by an interested listener. Individuals with depression and anxiety typically feel enhanced rather than diminished by these interviews. Nevertheless, several precautions will be taken to prevent stress from developing during the interview.

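### Aim 3 is given two different ANOVA descriptions and no missing-visit rule; in its usual form the repeated measures version would discard observed month-4 data and could bias the changes in either direction

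*Combined protocol and SAP*

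**What the plan says.** Section 8 (Procedures Involved) sets the visits: "Participants will be assessed at three time points (before starting the study, 4, and 7 months after the first interview". Section 10 (Data Management) then describes the Aim 3 analysis in two ways.

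- First: "a one-way ANOVA will be used to illustrate the change in scores from baseline to post-intervention in all the outcome measures used". This involves two visits.
- Next: "A repeated measures ANOVA, as we have proposed, is appropriate to explore the intervention effects". The supporting reason is that the method is often used for mean scores over three or more time points, which brings in month 7. Age, SES and years of education are to be covariates.

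The target is 18 men in a single group ("Successful recruitment will be defined as meeting 100% of targeted sample (N = 18"). The one retention criterion concerns month 4: "Adequate retention will be defined as 85% or more of randomized subjects completing the post-intervention assessment". No criterion is given for month 7.

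On software, section 9 (Data and Specimen Banking) says only: "Data will be exported to SPSS for analysis". Section 12 (Withdrawal of Subjects) allows gaps in the questionnaires: "Participants will be told that they may choose not to answer any questions". Section 8 also lets interviews move to the telephone, which cannot supply waist circumference, blood pressure or a blood sample.

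No section names an analysis set, a rule for missing visits or items, imputation, a mixed model or a sensitivity analysis.

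**The concern.** The two descriptions can use different men. A baseline-to-post-intervention comparison needs two values per man. A three-visit repeated measures ANOVA in its usual form needs all three, so a man seen at baseline and month 4 but not at month 7 drops out of every contrast, including the month-4 one for which he has data. The plan does not say which analysis supplies the reported change, or which men it covers.

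Two things are at stake. Observed data are thrown away in a study where each man is 1/18 = 5.6% of the sample. And the month-4 change would be estimated in men selected for still being present at month 7. If staying is related to how a man responded, that estimate is distorted, and it may inform the design of the larger trial.

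**Working it through.** The plan gives no power calculation, effect size or SD, so there is no stated figure to reproduce. Sizes below are in SD units.

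**1. How many men may lack month 4.** From section 10: N = 18, threshold 85%. 0.85 × 18 = 15.3, so at least 16 men are needed (15/18 = 83.3% fails; 16/18 = 88.9% passes). The criterion can be met with up to 2 men missing at month 4.

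**2. How many more are lost from a three-visit analysis.** Month-7 retention is not in the documents. Assume 85-95% of the 16 men seen at month 4.

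- 16 × 0.85 = 13.6 complete, so 2.4 men with month-4 data are left out.
- 16 × 0.95 = 15.2 complete, so 0.8 are left out.

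That is about 1-2 men.

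**3. Precision.** Half-width of the 95% CI for a mean change, in SDs of change = t(0.975, n − 1)/√n.

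- n = 16: 2.131/4.000 = 0.533.
- n = 14: 2.160/3.742 = 0.577.

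**4. Possible bias in the month-4 change.** Assume 10-15% of men are lost at month 7, with the log-odds of loss changing by 1-2 per SD of the variable that drives it. Where baseline drives loss, assume a baseline to month-4 correlation of 0.6. A negative sign means the completers' mean looks better than the truth.

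| What drives loss (assumed) | Bias in completers' mean change, SD of change |
|---|---|
| Nothing (random) | 0 |
| Poor month-4 response | −0.09 to −0.20 |
| Good month-4 response | +0.09 to +0.20 |
| Worse baseline value | +0.04 to +0.09 |

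**5. Cross-check by an identity.** Completers' mean − mean in all men = (share missing) × (completers' mean − non-completers' mean). If the two groups differ by 0.5-1.0 SD (assumed):

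- 2 of 18 missing: 0.111 × 0.5 = 0.06, to 0.111 × 1.0 = 0.11 SD.
- 5 of 18 missing: 0.278 × 0.5 = 0.14, to 0.278 × 1.0 = 0.28 SD.

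The sign follows the sign of the gap, and a zero gap gives zero bias. The order of magnitude agrees with step 4.

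**The case against.** **The plan never says that incomplete cases are dropped.** Correct. Deletion is how the method usually behaves, and section 9 names SPSS without a procedure. But nothing in the plan prevents it, and there is no missing-data rule to fall back on.

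**The first-named analysis does not need month 7.** Also correct. A reader might infer that all Aim 3 changes would come from full completers only. The documents do not support that, because on the baseline-to-post-intervention description a man seen at month 4 stays in. What remains is that the next sentence says a repeated measures ANOVA is what was proposed, and the two are not reconciled.

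**Results will lean toward improvement.** This is the tempting stronger reading. Section 13 (Risks to Subjects) withdraws men who become suicidal or psychotic, and section 12 lets men leave if procedures upset them, so a favourable lean is plausible for depression and anxiety. But the documents give no figures on why men leave, and the table above shows that the sign reverses under equally simple assumptions.

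**The 85% figure shows that loss is expected.** It is a feasibility threshold, not a forecast. The plan also has features that may limit loss: payments rising from $15 to $35, a telephone fallback for interviews, and twice-monthly booster walks between months 4 and 7.

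**The F test would be too liberal because sphericity fails.** This rests on assumed correlations. The plan neither states an alpha nor says the test goes uncorrected, so the point is not pressed.

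**Aim 3 is exploratory, and the study is not powered to test a hypothesis.** This stands and limits the consequence. No feasibility criterion in section 10 depends on the choice of analysis.

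**Conclusion.** The point holds in a limited form. Aim 3 has two unreconciled analyses and no rule for missing visits. One of them, run in its usual complete-case form, would discard the observed month-4 data of about 1-2 men, at a cost of roughly 0.04 SD in CI half-width (0.577 − 0.533). It could also shift the reported month-4 change by about 0.09-0.20 SD either way if loss depends on response, by less if loss depends on baseline, and not at all if loss is random. Even 0.20 SD is under half the half-width of the interval.

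These sizes rest on assumed month-7 retention and assumed dropout mechanisms; the documents supply neither. They support a statement that the changes may be biased, not a statement about direction. The change is still worth making, because a better method is available at almost no cost.

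**What to change.** In section 10, replace both descriptions with one Aim 3 analysis:

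- a linear mixed model per outcome, with visit (baseline, month 4, month 7) as a categorical fixed effect, a stated within-man covariance structure and small-sample degrees of freedom;
- all observed visits of all enrolled men as the analysis set;
- month-4 and month-7 changes from baseline with 95% CIs, and the number of men contributing at each visit;
- baseline values compared between men with and without all visits;
- a sentence saying that the model removes bias from dropout only if data are missing at random.

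SPSS, already named in section 9, has a mixed-model procedure. No visit, measurement or sample size changes. The cost is a revision of the analysis wording and slightly more analysis work.
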